
patients with severe thalassemia than in <-year-old patients, and most of the patients at the age of > 19 years lose the opportunity of HSCT. The economic and social development of our province has been in a backward state for a long time, and there are many patients with severe thalassemia who are not eligible for transplantation due to the non-standard treatment of thalassemia and the lack of MUD donors. Therefore, finding a safer, more effective and low-cost treatment strategy for such patients with severe thalassemia who are not eligible for transplantation is a key problem in the prevention and treatment of thalassemia in our province and even in the whole country and the world.

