The center is the earliest unit in our province to carry out HSCT treatment of hematological diseases, and the technical level of HSCT is in the leading position in the province, and it has a solid clinical application conditions and foundation. We are willing to accept and adopt the new concept and treatment of hypertransplantation in [name] team, and carry out clinical research on the treatment of thalassemia major under the guidance and help of [name], verify its "safety and efficacy", cure patients and promote the continuous development of science, and create a safe and effective new treatment model for the treatment of thalassemia major without pretreatment, reproductive damage, and post-transplant complications.

2. Research objectives

It is planned to recruit 3-5 patients with thalassemia major without HSCT indication and unable to undergo thalassemia gene therapy from June 01, 2024 to June 2025, and use the super transplantation treatment plan of [name] team to observe the cell reinfusion response, hematopoietic remodeling, hemoglobin level and blood transfusion, thalassemia clonal clearance, immune reconstitution, endocrine function recovery, gastrointestinal function recovery, infection and other complication rates. To verify the safety and efficacy of super transplantation in the treatment of thalassemia major.

3. Research design and methodology

(1) Research Design:

1. This study is a single-center, single-arm, prospective clinical study. There is no control and no blinding.

2. Subject recruitment and management

1) Patient recruitment: The center publishes recruitment information to screen patients who meet the inclusion criteria;

2) Patients were enrolled after signing the informed consent form;

3) Check the inclusion criteria: Subjects are included in strict accordance with the inclusion criteria, and if there is any situation described in the exclusion criteria, the subjects will be excluded in a timely manner, and a special person will be responsible for checking and recording relevant information.

4) Collect medical history and complete the personal information and medical history part of the study record form.

3. Lifestyle requirements

Patients should be on a hyperbaric sterile diet from the beginning of the super graft

process, and dietary hygiene should be observed. Different stages of the period have different dietary requirements, and subjects and their families should follow the arrangements of medical staff.

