4. Withdrawal criteria for subjects

The study physician and the sponsor may also request to stop or withdraw from this study for the following reasons:

- (1). Serious safety problems occur during the test;
- (2). There are serious complications that the investigator deems necessary to terminate the trial treatment;
- (3). From the perspective of the patient's interests, the best choice for the investigator is to terminate the trial treatment;
- (4). The subject withdraws the informed consent or actively asks to withdraw;
- (5) The subject has progressed and is no longer suitable to participate in this study;
- (6). The subject had poor compliance during the trial, refused to cooperate with the treatment and follow-up, and could not continue the study.

Subjects will still be provided with appropriate treatment options after withdrawing from the pilot study, and subjects can withdraw from the study without discrimination or retaliation after notifying the investigator at any stage of the trial, and any medical treatment and rights will not be affected as a result. After withdrawing from the study, the subjects will still be informed in detail of the appropriate medical plan for continuation, and the subjects will still be regularly followed up and guided to guide the follow-up treatment of the patients.

5. Description of the study intervention

This study is a prospective, single-center, single-arm clinical study, and it is planned to include 3-5 patients with thalassemia major who have no HSCT indication and cannot receive thalassemia gene therapy. The diagnosis of thalassemia major was determined by the thalassemia genotype and the clinical manifestations of the patients, and the patients who met the inclusion criteria and did not meet the exclusion criteria were screened and enrolled and received super transplantation therapy. Hypertransplantation is an innovative treatment plan of [name] team, which uses hematopoietic stem cell transplantation from healthy donors with the same haplotype as the patient, and observes the patient's cell reinfusion response, hematopoietic reconstitution, hemoglobin level and blood transfusion, thalassemia clonal clearance, immune

reconstitution, endocrine function recovery, gastrointestinal function recovery, as well as the incidence of graft-versus-host disease, infection and other complications after transplantation.

The duration of follow-up was 24 months. Follow-up visits include:

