In this study, descriptive statistics and multivariate regression analysis were used, absolute numbers were used for categorical data, and median data were used for continuous data, and chi-square test and nonparametric test were mainly used, $p < 0.05$ was statistically significant.

and (2) analysis of primary and secondary study endpoints

(3) Safety analysis

AEs were coded and calculated, which could be expressed in terms of severity, frequency, and association with the intervention. Adverse events leading to discontinuation of study intervention and serious AEs resulting from treatment should be listed individually.

(4) Baseline descriptive analysis

Descriptive statistics were used to compare demographic characteristics and laboratory indicators at baseline between groups.

(5) Subgroup analysis

The study endpoints could be analyzed according to the transplantation conditioning regimen, pre-transplantation remission status, age, neutrophil and platelet engraftment

time, etc., and the association between the primary and secondary study endpoints and different factors could be evaluated by COX regression.

10. Quality control and quality assurance

In order to ensure that the trial can be carried out in strict accordance with the clinical research protocol, in the process of clinical trial, the clinical investigator, the sponsor and the clinical supervisor should operate in accordance with the requirements of the clinical trial quality management practice, and must ensure that the test procedures are standardized, the experimental data are accurate, the experimental data are traceable, and the research conclusions are reliable.

IV. Inclusion and exclusion guidelines

(1) Patient enrollment criteria:

Patient inclusion criteria (the following 4 criteria must be fully met):

- 1) Confirmed diagnosis of thalassemia major, regardless of α and β type;
- 2) Age between 7-12 years old, male or female; Weight < 40kg
- 3) Patients with or without HLA-matched or haploidentical donors, but unconditionally transplanted or refused to undergo blood stem cell transplantation; Patients who are unconditional or refuse to undergo thalassemia gene therapy;
- 4) There are HLA fully compatible or incompatible donors, and the physical examination meets the donor conditions;
- 5) The patient and his or her family agree to receive ultra-transplantation therapy and sign a written informed consent form before the transplantation trial.

(2) Patient exclusion criteria:

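### Inclusion criterion 3 admits children for whom HSCT or gene therapy is refused, a group that the objective and the intervention section do not name

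*Protocol*

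**What the plan says.** Section 2 of the protocol (Research objectives) plans to recruit "patients with thalassemia major without HSCT indication and unable to undergo thalassemia gene therapy". Section 3.(1) 5 (Description of the study intervention) repeats this: "3-5 patients with thalassemia major who have no HSCT indication and cannot receive thalassemia gene therapy". The background asks for a "treatment strategy for such patients with severe thalassemia who are not eligible for transplantation", having described patients as "not eligible for transplantation due to the non-standard treatment of thalassemia and the lack of MUD donors".

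Inclusion criterion 3 in section IV.(1) has two limbs. The first covers HSCT: "Patients with or without HLA-matched or haploidentical donors, but unconditionally transplanted or refused to undergo blood stem cell transplantation". The second covers gene therapy: "Patients who are unconditional or refuse to undergo thalassemia gene therapy".

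The criteria govern who is treated. According to the intervention section, "the patients who met the inclusion criteria and did not meet the exclusion criteria were screened and enrolled and received super transplantation therapy". The recruitment paragraphs, in section 3.(1) 2 and again under subject protection measures, require strict adherence to the inclusion criteria.

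**The concern.** Eligibility criteria normally narrow the population named in the objective. Here they widen it. Declining a treatment that is available is different from having no indication for it or being unable to receive it, and criterion 3 itself treats the two as alternatives by joining them with *or*.

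The main indicators are donor cell engraftment and transplant-related death, both at 3 months, in 3-5 children with no control group. The value of such a series depends largely on saying exactly who was treated. If some of the children could have had HSCT or gene therapy, a reader who takes the objective at its word would apply the results to a different group.

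The protocol's own background suggests why the distinction matters. It gives 80-87% 5-year survival for HSCT from haplotype donors, with more complications. A child for whom HSCT is refused may have that alternative; a child with no HSCT indication does not. The results would be weighed against different alternatives in the two groups.

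**Working it through.** The protocol gives no calculation on this point, so the check sets the texts side by side.

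**Step 1: who is named where.**

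| Place in the protocol | HSCT condition | Gene-therapy condition | Refusal named? |
|---|---|---|---|
| Background (rationale) | Not eligible; the sentence gives non-standard treatment and lack of MUD donors as reasons | None | No |
| 2. Research objectives | No indication | Unable to undergo | No |
| 3.(1) 5. Intervention | No indication | Cannot receive | No |
| IV.(1) Inclusion 3 | Lacks the conditions, *or* refuses; with or without a matched or haploidentical donor | Lacks the conditions, *or* refuses | Yes, in both limbs |

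The entry for lacking the conditions is a charitable reading of rough translation. On that reading, this route can be squared with the objective. The refusal route cannot.

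**Step 2: does the link between the two limbs matter?** A semicolon separates them, and the text does not say whether both are required. If both are required, each limb has two routes, which gives 2 × 2 = 4 combinations. Only one of these (lacks the conditions for both treatments) fits the objective. The other three involve refusal of at least one treatment. If either limb is enough, the criterion is wider still. Refusal is admitted under both readings.

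**Step 3: do the exclusions remove such a child?** Exclusions 1 to 3 in section IV.(2) concern psychiatric illness, recent participation in another drug trial, and lack of a suitable HLA-incompatible donor. None concerns refusal. Exclusion 4 leaves suitability to the investigator's judgement and sets no rule.

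**Step 4: size.** One child as a share of the planned sample:

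- n = 5: 1/5 = 20%
- n = 4: 1/4 = 25%
- n = 3: 1/3 = 33%

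The criteria set no limit on the number of such children, so the share ranges from 0/n = 0% to n/n = 100%.

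**Step 5: donor definition (secondary).** Inclusion 4 accepts a donor who is either fully compatible or incompatible. Exclusion 3 appears to rule out a child who has no suitable HLA-incompatible donor. Donor criterion 1 in section IV.(3) and the intervention section specify a donor sharing the patient's haplotype. Read literally, a child whose only donor is fully compatible meets inclusion 4 and is then removed by exclusion 3. Allowing for translation, these passages still do not give one definition.

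**The case against.** The strongest reply is that nobody enrolling patients would be in doubt. The criteria are the operative rule, and the objective is a one-line summary that happens to leave out one route. On that view this is a wording repair. It is true that the repair is one of wording. But the summary is the protocol's statement of whom the trial is about, and it appears twice in the same narrow form.

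Second, the translation is unreliable, and having no HSCT indication sits oddly with a background that calls HSCT the only clear cure. This does leave some doubt about how narrow the stated population was meant to be. It does not remove the word for refusal, which appears in both limbs of criterion 3.

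Third, the document offers grounds for treating refusers. The objectives close with a broad aim, "To verify the safety and efficacy of super transplantation in the treatment of thalassemia major", and the background describes conditioning toxicity, GVHD, reproductive harm and cost, any of which could lead a family to decline HSCT. This stands: it cannot be said that the trial is unjustified for these children. It also means that the document does not settle which population is intended.

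Fourth, the 80-87% figure is not given for children aged 7-12, and the background says that HSCT does less well above an age that is not legible in the text at hand, and describes heart damage and hepatic iron. The figure therefore cannot be assigned to any particular child in this trial. It shows only that the protocol itself describes an alternative that one group may have and the other lacks.

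Finally, the shares in the check follow from the sample size alone, and no changed result is shown. That is correct; they indicate scale and nothing more.

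**Conclusion.** The concern holds. Following the protocol as written can enrol children outside the population named in its objective and intervention section. This is a contradiction between sections and cannot be left to a statistical analysis plan, because the protocol fixes eligibility. Each such child would make up 20% to 33% of the sample, and their number is neither stated nor limited.

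The conclusion assumes that the odd wording in criterion 3 means lacking the conditions for treatment, and that refusal means what it says. It does not assume that refusal affects engraftment or transplant-related death, and it does not say which population is right. It should be fixed, ideally before enrolment. The inconsistent donor definition is a lesser point of the same kind, since it also changes who can enter.

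**What to change.** Reconcile the background, the research objectives, the intervention section and inclusion criterion 3 so that all name one population, the sponsor deciding which. State in criterion 3 whether the HSCT and gene-therapy limbs are both required.

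If refusers stay eligible, say so in the objective, record at screening each child's reason for having no HSCT and no gene therapy, and identify these children in the results. With 3-5 patients, a line in the individual patient listing is enough.

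In the same amendment, bring inclusion 4, exclusion 3, donor criterion 1 and the intervention section to one donor definition, again for the sponsor to decide. As an editorial matter, the heading of the inclusion list announces four criteria, but five follow.

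The cost is a short text amendment. Leaving refusers out may slow recruitment slightly; keeping them means a broader stated objective.
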